3.2.1 Hypotheses

The primary effectiveness objective is to demonstrate that the primary effectiveness event-free rate through 12 months post-procedure is greater than the specified performance goal.

H_0 : The primary effectiveness event-free rate at 12 months post-procedure $\leq 50\%$ ²⁷

H_a : The primary effectiveness event-free rate at 12 months post-procedure $> 50\%$

3.2.2 Sample Size

The sample size estimate was obtained using the normal approximation to the binomial distribution and verified through simulations based on Kaplan-Meier methodology. The following assumptions were used in the sample size calculation:

Assumptions	Primary Effectiveness
Expected rate	60% ^{26,28,29}
Performance goal	50%
Attrition (per year)	7.5%
Significance level (one-sided)	5%
Power	80%

Under the hypothesis and assumptions outlined above, the required sample size for this endpoint is 183 TREATMENT subjects.

3.2.3 Statistical Methods

For the primary effectiveness endpoint, the Kaplan-Meier 12 month (365-day) primary effectiveness event-free rate will be calculated. Subjects who die or withdraw from the study prior to 12 months without experiencing an endpoint event will be censored on the date of death or the date of withdrawal. The 95% one-sided lower confidence limit of the observed primary effectiveness event-free rate will be compared to the performance goal of 50%. If the lower confidence limit is greater than the performance goal, the null hypothesis will be rejected. The lower confidence limit will be calculated as the pointwise confidence limit using the log-log methodology.

3.3 Secondary Effectiveness Endpoint

The secondary effectiveness endpoint is defined as the event-free at 12 months post-procedure.

Secondary effectiveness events are defined as:

- Acute procedural failure
- More than one repeat procedure during the blanking period (90 days post index procedure)
- Documented symptomatic atrial fibrillation, or new onset of atrial flutter or atrial tachycardia event (\geq 30 seconds in duration from an event monitor or Holter, or from a 10 second 12-lead EKG) between 91 days and 365 days post index procedure
- Any of the following interventions for atrial fibrillation, or new onset of atrial flutter or atrial tachycardia between 91 days and 365 days post index procedure:
 - Repeat procedure
 - Cardioversion
 - Prescribed a higher dose of any AAD* documented at baseline
 - Prescribed a new AAD* not documented at baseline

*AADs for endpoint will consist of all Class I/III and any Class II/IV medications taken for control of AF/AT/AFL recurrence

3.3.1 Hypotheses

The secondary effectiveness objective is to demonstrate that the secondary effectiveness event-free rate through 12 months post procedure is greater than the specified performance goal.

H_0 : The secondary effectiveness event-free rate at 12 months post-procedure \leq 50%

H_a : The secondary effectiveness event-free rate at 12 months post-procedure $>$ 50%

3.3.2 Sample Size

The sample size estimate was obtained using the normal approximation to the binomial distribution and verified through simulations based on Kaplan-Meier methodology. The following assumptions were used in the sample size calculation:

Assumptions	Secondary Effectiveness
Expected rate	65% ²⁶
Performance goal	50%
Attrition (per year)	7.5%
Significance level (one-sided)	5%
Power	80%

Under the hypothesis and assumptions outlined above, the required sample size for this endpoint is 83 TREATMENT subjects.

3.3.3 Statistical Methods

For the secondary effectiveness endpoint, the Kaplan-Meier 12 month (365-day) secondary effectiveness event-free rate will be calculated. Subjects who die or withdraw from the study prior to 12 months without experiencing an event will be censored on the date of death or the date of withdrawal. The 95% one-sided lower confidence limit of the observed secondary effectiveness event-free rate will be compared to the performance goal of 50%. If the lower confidence limit is greater than the performance goal, the null hypothesis will be rejected. The lower confidence limit will be calculated as the pointwise confidence limit using the log-log methodology.

3.4 Tertiary endpoint

Chronic Effectiveness: Evaluation of chronic recurrence at 24 months and 36 months

- Recurrence is defined as intervention for atrial fibrillation, or new onset of atrial flutter or atrial tachycardia (repeat procedures, use of AADs, cardioversion), excluding repeat procedures during the 90-day blanking period.
- Data collection to include the diagnostic modality used to identify recurrence and the therapeutic intervention
- Chronic effectiveness will be evaluated using Kaplan-Meier methodology. The Kaplan-Meier 24 month and 36 month chronic recurrence-free rate will be calculated and presented along with the 95% confidence interval, calculated as the pointwise confidence limit using the log-log methodology. Subjects who die or withdraw from the study prior to the specified time point without experiencing an event will be censored on the date of death or on the date of withdrawal.

Center Experience: Primary safety and Primary effectiveness outcomes by center experience

- In order to evaluate training effectiveness for investigators outside of the ZERO AF IDE study, outcomes in centers performing five or more procedures using the Blazer OI catheter during the ZERO AF IDE study will be compared to all other. Kaplan-Meier rates and 95% confidence intervals for the Primary Safety and Effectiveness endpoints for both groups will be presented with no statistical comparison.

Safety: Reportable Adverse Events rates at 12, 24 and 36 months

Adverse events will be collected at all subject follow-up visits. Reportable events include:

- All Serious Adverse Events
- All Study Procedure-Related Adverse Events
- All Study Device-Related Adverse Events
- All Study Device Deficiencies
- Unanticipated Adverse Device Effects/Unanticipated Serious Adverse Device Effects previously not defined in the Directions For Use.

Adverse event rates will be calculated using binomial methodology. The cumulative number of events and event rate will be included in all study reports. Subjects at risk for an adverse event will be determined by the subject treatment status; all treatment and attempt subjects will be considered at risk for study related adverse events

Effectiveness: Acute Procedural Success Rate

Acute Procedural Success is defined as pulmonary vein isolation achieved with a Boston Scientific OI ablation catheter as demonstrated by map-based entrance block with exit block and other maneuvers (such as adenosine testing) at the discretion of the physician.

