#### **8.4.1. Medications**

#### **8.4.2. Anti-Arrhythmic Drugs**

It is recommended that all Anti-Arrhythmic Drugs (AADs) should be stopped at least five half-lives before the procedure; amiodarone should be stopped one month before the procedure.

It is recommended that AADs only be prescribed after the procedure if a subject has a documented arrhythmia recurrence. Post-procedure AADs are allowed per physician's discretion but new AADs should not be prescribed unless considered medically necessary. At eight weeks, investigators should remove subjects from AADs to appropriately assess the subject for early arrhythmia recurrence that may require a repeat ablation procedure within the blanking period (on or before day 90)

If the investigator determines that the subject must remain on an AAD after the blanking period, the subject will be considered a Primary Effectiveness Failure.

Treatment with Class II/IV medications for conditions other than control of arrhythmia recurrence is also permitted and will be documented. Every effort should be made to keep those drugs at a stable dose over the entire course of the study.

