#### 9.1.4. Tertiary Endpoint

##### **Chronic Effectiveness:** Evaluation of chronic recurrence at 24 months and 36 months

- Recurrence defined as intervention for atrial fibrillation, or new onset of atrial flutter or atrial tachycardia (repeat procedures, use of AADs, cardioversion), excluding repeat procedures during the blanking period.
- Data collection to include the diagnostic modality used to identify recurrence and the therapeutic intervention
- Chronic effectiveness will be evaluated using Kaplan-Meier methodology. The Kaplan-Meier 24 month and 36 month chronic recurrence-free rate will be calculated and presented along with the 95% confidence interval, calculated as the pointwise confidence limit using the log-log methodology. Subjects who withdraw from the study prior to the specified time point without experiencing an event will be censored on the date of withdrawal.

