**Table 11: Definitions**

Term	Definition
Ablation Attempt	One or more RF ablations targeted at a single gap closure. An attempt is considered complete once isolation is tested.
Activated Coagulation/Clotting Time	ACT is a test that is used to monitor the effectiveness of high dose heparin therapy.
Arterial-Venous Fistula	Abnormal communication between an artery and a vein.
Atrio-Esophageal Fistula	A connection between the atrium and the lumen of the esophagus
ATTEMPT Subject	Any subject that signs the consent form, meets eligibility criteria and has any study device inserted into the body but does not receive RF ablation per protocol.
AV block	A conduction disturbance that results in the partial inability of an electrical impulse generated in the atria to reach the ventricles.
Blanking Period	90-day period between ablation procedure and the initiation of the Effectiveness Evaluation Period during which up to one additional ablation procedures can be performed and subjects can be prescribed antiarrhythmic drugs as determined necessary by the investigator.

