3.2 Primary Effectiveness Endpoint

The primary effectiveness endpoint will be evaluated by the primary effectiveness event-free rate at 12 months post-procedure.

Primary effectiveness events will be defined as the following:

- Acute procedural failure
- More than one repeat procedure during the blanking period (90 days post index procedure)
- Documented atrial fibrillation, or new onset of atrial flutter or atrial tachycardia event (≥ 30 seconds in duration from an event monitor or Holter Monitor, or from a 10 second 12-lead EKG) between 91 days and 365 days post index procedure
- Any of the following interventions for atrial fibrillation, or new onset of atrial flutter or atrial tachycardia between 91 days and 365 days post index procedure:
 - Repeat procedure
 - Cardioversion
 - Prescribed any AAD*

*AADs for endpoint will consist of all Class I/III and any Class II/IV medications taken for control of AF/AT/AFL recurrence

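### The 24- and 36-month chronic recurrence definition blanks only repeat procedures, so as written AAD use or cardioversion for AF/AFL/AT in days 0–90 counts as chronic recurrence

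*SAP*

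**What the plan says.** SAP 3.4 defines chronic recurrence as an intervention for AF, or for new-onset atrial flutter (AFL) or atrial tachycardia (AT), and completes the definition with "repeat procedures, use of AADs, cardioversion), excluding repeat procedures during the 90-day blanking period". The protocol synopsis and protocol 4.4 carry the same clause. Protocol 9.1.4 drops only the length of the period: "repeat procedures, use of AADs, cardioversion), excluding repeat procedures during the blanking period". None of the four gives a start day for AAD use or cardioversion. The result is a Kaplan-Meier recurrence-free rate at 24 and 36 months with a 95% log-log interval.

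The primary effectiveness endpoint (SAP 3.2) counts a repeat procedure, a cardioversion or any AAD when they are "interventions for atrial fibrillation, or new onset of atrial flutter or atrial tachycardia between 91 days and 365 days post index procedure". SAP 3.3 sets the same window for the secondary endpoint, where the AAD criterion is a new drug or a dose above baseline. Both endpoints also count acute procedural failure and "More than one repeat procedure during the blanking period (90 days post index procedure").

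Protocol Table 11 describes the blanking period as the "90-day period between ablation procedure and the initiation of the Effectiveness Evaluation Period", in which "subjects can be prescribed antiarrhythmic drugs as determined necessary by the investigator". Protocol 8.4.2 leaves post-procedure AADs to the physician and then says: "At eight weeks, investigators should remove subjects from AADs". If the investigator decides that a subject "must remain on an AAD after the blanking period, the subject will be considered a Primary Effectiveness Failure". Protocol 8.8 treats AAD changes made at the three-month visit, whose window runs to day 120, as falling within blanking.

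**The concern.** The definition lists three interventions and exempts one of them during blanking. The ordinary reading is that the other two count from day 0. No reason is given for the distinction, and its effect is odd: a re-ablation on day 60 is not a chronic recurrence, but a cardioversion on day 20 is.

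The literal rule also treats as chronic failure something that the protocol permits and expects to be temporary, namely an AAD given for early AF and withdrawn around week eight.

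What is at stake is the study's long-term effectiveness figure. An analyst who follows the words and one who follows the probable intent would report different 24- and 36-month rates from the same data. Under the literal rule, some subjects who are event-free at 12 months on the primary endpoint would already be failures on the chronic curve.

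**Working it through.** **1. The definitions side by side, days 0–90 only**

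| Endpoint | Repeat procedure | Cardioversion for AF/AFL/AT | AAD for AF/AFL/AT |
|---|---|---|---|
| Chronic recurrence, as written (SAP 3.4; protocol synopsis, 4.4, 9.1.4) | not counted | counted | counted |
| Primary (SAP 3.2) | counted only if more than one | not counted | not counted |
| Secondary (SAP 3.3) | counted only if more than one | not counted | not counted |

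The mismatch is confined to the last two columns. In the first column the chronic endpoint is the more lenient one.

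**2. One subject followed through.** Acute success; AAD started for AF on day 20 and stopped by week eight (day 56); no later arrhythmia or intervention.

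- Primary endpoint: event-free at day 365.
- Chronic endpoint as written: event on day 20, so a failure at 24 and 36 months.
- Chronic endpoint with all three interventions counted from day 91: event-free.

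**3. Size.** The documents state no expected rate, sample size or power for this endpoint, so there is no planned figure to reproduce. Let

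- *S* = recurrence-free rate at the time point when all three interventions count from day 91;
- *a* = share of subjects with AAD use or cardioversion for AF/AFL/AT in days 0–90.

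The documents give neither, so both are assumptions. To be recurrence-free under the literal rule, a subject must be free of recurrence from day 91 and must also have had no such intervention in days 0–90. Ignoring censoring, the literal rate therefore lies between

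- lower bound *S* − *a* (no affected subject recurs later), and
- upper bound min(*S*, 1 − *a*), which equals *S* throughout the table (every affected subject also recurs by the time point),

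and it equals *S*(1 − *a*) if the two are independent.

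| Assumed *S* | *a* = 5% | *a* = 10% | *a* = 20% |
|---|---|---|---|
| 50% | 45–50% (47.5%) | 40–50% (45%) | 30–50% (40%) |
| 60% | 55–60% (57%) | 50–60% (54%) | 40–60% (48%) |
| 70% | 65–70% (66.5%) | 60–70% (63%) | 50–70% (56%) |

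Independence is in brackets. For example, with *S* = 60% and *a* = 10%: 0.60 − 0.10 = 0.50 and 0.60 × 0.90 = 0.54. At the planned minimum of 329 TREATMENT subjects, each affected subject who never recurs later costs 1/329 = 0.30 points before censoring.

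**4. Role in study success.** Protocol 9.2.3 and SAP 4.3 tie success to the two primary endpoints and gate only the secondary one. The chronic endpoint has no hypothesis, performance goal or alpha.

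**The case against.** The strongest reply is that the intent is clear enough. Table 11 places blanking before effectiveness evaluation begins. Protocol 8.4.2 and 10.4.1.1 describe arrhythmia in that window as early recurrence, while this endpoint is labelled chronic. Protocol 15.1 treats an intervention for recurrence as a serious adverse event only after day 90, without singling out repeat procedures. Because the SAP supplements the protocol, an analyst has real support for starting at day 91. This stands as evidence of intent. It does not override an explicit exclusion that names one item of three: the Table 11 term is not tied to this endpoint, and 15.1 concerns safety reporting.

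It is also fair that the size rests on assumed inputs. Protocol 8.4.2 recommends post-procedure AADs only after documented recurrence, so affected subjects may well recur again. That would move the loss toward zero, and independence should not be taken as the central case.

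A reader might go further than the documents allow in four ways:

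- That every AAD taken in blanking is a chronic failure. The definition covers only interventions for AF or new-onset AFL/AT.
- That the primary and secondary endpoints ignore everything before day 91. They count acute procedural failure and more than one repeat procedure.
- That the SAP and protocol contradict each other on this endpoint. All four statements agree.
- That the chronic endpoint must mirror the primary one. It is an intervention-only measure and need not; what is missing is a reason for blanking one of its interventions and not the other two.

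**Conclusion.** The point holds as a defect in a stated counting rule. Applied exactly, the rule classes AAD use or cardioversion for AF/AFL/AT in days 0–90 as chronic recurrence, out of line with the day-91 start for the same interventions in the primary and secondary endpoints and with the Table 11 description of blanking.

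Compared with a day-91 start, the literal rule cannot raise the underlying recurrence-free rate. It lowers it by 0 to *a* points. Since the documents give no value for *a*, every percentage shown here is illustrative.

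The consequence is limited to a descriptive tertiary endpoint. A reader might infer that the trial's success criteria or error control are compromised; neither depends on this endpoint. It should still be fixed, because the rate is the study's long-term effectiveness result and the wording as it stands supports one number while the probable intent supports another.

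**What to change.** Before the 24-month analysis, change the clause in all four places (SAP 3.4; protocol synopsis, 4.4 and 9.1.4) to: *excluding repeat procedures, AAD use and cardioversion during the 90-day blanking period*. Then settle, for analysis purposes only, how AAD use at the edge of blanking is counted:

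- Apply the rule in protocol 8.8, so that an AAD stopped at the three-month visit (up to day 120) is not an event, and say that this takes precedence over the day-91 start.
- State whether an AAD started at that visit and continued counts, and whether any AAD continued past it counts.
- Fix one event date for such use, for example day 91 or the visit date, because Kaplan-Meier needs one.

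If the literal rule was intended, say so, give the reason, and also report the day-91 version.

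The cost is one clause and a short AAD-timing rule. SAP section 6 provides for changes through an amended SAP approved before the analysis. The definition also sits in the protocol, and protocol 12.3 requires ethics review of any protocol amendment. If the SAP is amended first, it should record that it departs from the protocol synopsis, 4.4 and 9.1.4 until the next protocol amendment. Medication regimen and interventions are already collected at follow-up visits (protocol Table 5 and 8.7 to 8.12). The documents do not say that AAD start and stop dates are recorded, so check the case report form before fixing the event date.

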##### **Center Experience:** Primary Safety and Primary Effectiveness outcomes by center experience

- In order to evaluate training effectiveness for investigators outside of the ZERO AF IDE study, outcomes in centers performing five or more procedures using the Blazer OI catheter during the ZERO AF IDE study will be compared to all other centers in the study. Kaplan-Meier rates and 95% confidence intervals for the Primary Safety and Effectiveness endpoints for both groups will be presented with no statistical comparison.

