1.5 Planned number of sites and patients

The study will enroll 415 global subjects (US, EU, Asia-Pacific) with 25-50 centers. A minimum of 50% of the enrolling sites will be selected from the US. No study site will be allowed to contribute more than 41 subjects (10% of total allowed).

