3.1.2 Sample size

The sample size estimate was obtained using the normal approximation to the binomial distribution and verified through simulations based on Kaplan-Meier methodology. The following assumptions were used in the sample size calculation:

Assumptions	Primary Safety
Expected rate	90% ²⁶
Performance goal	85%
Attrition (per year)	7.5%
Significance level (one-sided)	5%
Power	80%

Under the hypothesis and assumptions outlined above, the required sample size for this endpoint is 329 TREATMENT subjects.

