3.1.3 Statistical methods

For the primary safety endpoint, the Kaplan-Meier 12 month (365-day) primary safety event-free rate will be calculated. Subjects who withdraw from the study prior to 12 months without experiencing an event will be censored on the date of withdrawal. The 95% one-sided lower confidence limit of the observed safety event-free rate will be compared to the performance goal of 85%. If the lower confidence limit is greater than the performance goal, the null hypothesis will be rejected. The lower confidence limit will be calculated as the pointwise confidence limit using the log-log methodology.

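### The center-experience comparator is every center below five ZERO AF Blazer OI procedures, not centers outside ZERO AF, and no difference between the groups is planned

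*SAP*

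**What the plan says.** SAP 3.4 gives the aim as "In order to evaluate training effectiveness for investigators outside of the ZERO AF IDE study". The grouping rule follows at once: "outcomes in centers performing five or more procedures using the Blazer OI catheter during the ZERO AF IDE study will be compared to all other". Protocol 9.1.4 and the synopsis complete the phrase: outcomes in the experienced centers "will be compared to all other centers in the study". Protocol 4.4 uses the shorter SAP wording.

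The output is a Kaplan-Meier rate with a 95% confidence interval for primary safety and for primary effectiveness in each group. These results "for both groups will be presented with no statistical comparison".

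The study runs "with 25-50 centers", and "No study site will be allowed to contribute more than 41 subjects". Neither document states how many of these centers took part in ZERO AF, or with how many procedures.

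**The concern.** The aim names one population, investigators outside ZERO AF, and the rule defines another, all centers below a volume threshold. The two coincide only if no participating center performed between one and four Blazer OI procedures in ZERO AF. Otherwise the rate reported for the comparator is a mixture, and the plan never defines a rate for the population it set out to judge.

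The text also announces a comparison but plans no estimate of one. Leaving out a hypothesis test is reasonable at this level. Leaving out the difference and its interval is a separate choice, and it leaves the reader to judge by whether two intervals overlap. Overlap is a poor guide to a difference, and it does not show how large a training shortfall the data leave open.

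This is the plan's only analysis directed at training, in a post-approval study that FDA asked for.

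**Working it through.** **1. Is the gap filled elsewhere?** No. The subgroup covariates (SAP 5.2; Protocol 9.3.2) are sex, age, repeat procedure in the blanking period, ablation technique and DirectSense use. The center pooling test (SAP 5.3; Protocol 9.3.3) looks for variation between centers without regard to ZERO AF experience.

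**2. The plan's own figure.** The center-experience analysis has no stated sample size or precision. The only anchor is primary safety (SAP 3.1.2), where "the required sample size for this endpoint is 329 TREATMENT subjects". A one-sample exact binomial calculation (90% against 85%, one-sided 5%, 80% power maintained for every larger n) needs 304. Allowing for 7.5% attrition, 304 / 0.925 = 328.6, rounded up to 329. The figure reproduces and serves below only as a total to split.

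**3. Dilution.** Let E be the 12-month rate in experienced centers and N the rate in centers outside ZERO AF. Let f be the share of comparator subjects from ZERO AF centers with 1-4 procedures. None of these is given in the documents.

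- If the 1-4 centers perform like the experienced group, the comparator rate is fE + (1 - f)N, and the visible gap is E - [fE + (1 - f)N] = (1 - f)(E - N).
- If they perform like new centers, the comparator rate is N and the visible gap is E - N for any f.

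For an assumed true gap of 10 points:

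| f | 1-4 centers like experienced | 1-4 centers like new |
|---|---|---|
| 0% | 10 | 10 |
| 10% | 9 | 10 |
| 20% | 8 | 10 |
| 30% | 7 | 10 |
| 40% | 6 | 10 |

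If their performance lies between the two, so does the visible gap.

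**4. Precision of a difference.** Half-width = 1.96 × √[p(1 - p)(1/n1 + 1/n2)]. The rates are the plan's expected values, p = 0.90 for safety (SAP 3.1.2) and p = 0.60 for effectiveness (SAP 3.2.2), with n1 + n2 = 329. The split is assumed and censoring is ignored.

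| Share in experienced centers | n1 v n2 | Safety | Effectiveness |
|---|---|---|---|
| 10% | 33 v 296 | ±10.8 points | ±17.6 points |
| 20% | 66 v 263 | ±8.1 | ±13.2 |
| 30% | 99 v 230 | ±7.1 | ±11.5 |
| 50% | 164 v 165 | ±6.5 | ±10.6 |

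Worked row, 66 v 263, effectiveness: 1.96 × √[0.24 × (1/66 + 1/263)] = 0.132.

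**5. Why overlap misleads.** For the same 66 v 263 split, the separate half-widths for effectiveness are 1.96 × √(0.24/66) = 11.8 points and 1.96 × √(0.24/263) = 5.9 points, 17.7 in total. The half-width for the difference is 13.2. A gap of roughly 13 to 18 points would therefore show overlapping intervals although the interval for the difference excludes zero. For safety the separate half-widths are 7.2 and 3.6, 10.8 in total, against 8.1 for the difference.

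**6. Effect of splitting off the middle group.** If f = 20% in the 66 v 263 case, about 0.8 × 263 = 210 subjects remain in the no-procedure group. The half-width becomes 1.96 × √[0.24 × (1/66 + 1/210)] = 13.5 points for effectiveness, up from 13.2. For safety, 1.96 × √[0.09 × (1/66 + 1/210)] = 8.3, up from 8.1.

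**The case against.** The strongest reply is that the endpoint is headed as outcomes by center experience. On that heading, five procedures is a sensible prespecified threshold, with low-volume ZERO AF centers deliberately classed as not experienced. This is a fair reading of the threshold. It does not make every center below the threshold one outside ZERO AF, which is the population in the stated aim.

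A reader might infer that the comparator does contain ZERO AF centers with 1-4 procedures and that a real shortfall will be diluted. The documents do not support this. They give no count of centers by ZERO AF participation, so f may be zero, and dilution further requires those centers to perform better than new ones.

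A reader might also infer that the analysis cannot answer its question, or that the text contradicts itself by comparing without a comparison. Neither follows. Every place that describes the analysis sets out a side-by-side descriptive presentation. The two rates with intervals are informative and can be read beside the 85% and 50% performance goals. A careful reader can derive an approximate difference from them. Nothing in the plan says that overlap will be taken as proof that training works.

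Finally, reporting a difference does not cure imprecision, and a 95% interval can be used as an informal test. Both are true. They are reasons to label the interval descriptive, and the imprecision is itself worth showing.

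**Conclusion.** Two points stand. The comparator as defined does not match the stated aim, and no estimate of the gap or its uncertainty is planned.

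The first is a fault of definition whose numerical effect is unknown. It runs from nothing to a loss of a fraction f of the true gap, assuming the 1-4 centers perform no worse than new centers and no better than experienced ones. The second holds whatever f is. If 10-50% of 329 subjects are in experienced centers, the unreported half-width is about 6.5-11 points for safety and 11-18 for effectiveness. These figures rest on assumed splits, the plan's expected rates and no censoring. The planned 7.5% yearly attrition would widen them somewhat.

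Severity is low. The endpoint is tertiary and descriptive, lies outside the success rule and the gated testing (SAP 3 and 4.3), and cannot change a primary or secondary conclusion.

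**What to change.** In SAP 3.4, present Kaplan-Meier rates with 95% confidence intervals for three groups of centers: at least five ZERO AF Blazer OI procedures, 1-4, and none. If no center falls in the middle group, say so. Give the number of centers and subjects in each group. For the first group against the last, report the difference in 12-month rates with a two-sided 95% confidence interval from the Greenwood standard errors, labelled descriptive and without a p-value.

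The change needs only each center's ZERO AF procedure count, which the existing rule already requires, and it spends no alpha. The costs are a middle group that may be small, a slightly wider interval because that group leaves the contrast, and an imprecise result that becomes visible. The same text in the protocol synopsis, 4.4 and 9.1.4 must be aligned, and Protocol 12.3 requires ethics review of any protocol amendment. SAP 6 already provides for an amended SAP approved before the analyses are run.
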